9.2 SECONDARY ENDPOINTS

Secondary endpoints will be compared between randomized groups in an analogous fashion to the primary efficacy endpoint [REDACTED]

Safety will be reported as the incidence of all serious device/procedure related AEs, as adjudicated by an independent clinical events adjudicator. The adjudicated events will be coded using the Medical Dictionary for Regulatory Activities (MedDRA). This endpoint will be tabulated and reported by randomized group. A summary of all reported AEs will also be provided.

[REDACTED]				
[REDACTED]	[REDACTED]	[REDACTED]	[REDACTED]	[REDACTED]
[REDACTED]	[REDACTED]	[REDACTED]	[REDACTED]	[REDACTED]
[REDACTED]	[REDACTED]	[REDACTED]	[REDACTED]	[REDACTED]
[REDACTED]	[REDACTED]	[REDACTED]	[REDACTED]	[REDACTED]

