12. Grade II or higher spondylolisthesis.
13. Motor deficit or disabling back and/or leg pain from causes other than LSS neurogenic claudication (e.g. acute compression fracture, metabolic neuropathy, or vascular claudication symptoms, etc.).
14. Unable to walk \geq 10 feet unaided before being limited by pain. In this context, 'unaided' means without the use of a cane, walker, railing, wall, another person or any other means of walking assistance.
15. Previously randomized and/or treated in a similar clinical study.
16. Epidural lipomatosis (if it is deemed to be a significant contributor of canal narrowing by the medical monitor and the treating physician).
17. On (or pending) Workman's Compensation or in active litigation or known to be considering litigation associated with back pain.

Statistical Analysis:

Continuous data will be summarized using descriptive statistics: mean, standard deviation, median, minimum and maximum. Categorical variables will be summarized using frequency counts and percentages. For events that can occur more than once in a single subject (e.g., adverse events), the percentage will be based on subjects experiencing the event, and both patient and event counts will be reported. All hypothesis testing will be performed using a two-sided test at a 0.05 level of significance or a one-sided test at a 0.025 level of significance.

[figure not shown]
[figure not shown]
[figure not shown]
[figure not shown]
[figure not shown]
[figure not shown]
[figure not shown]
Data will be analyzed on an Intent-to-Treat basis, under which analyses will be performed according to randomized assignment irrespective of the treatment actually received.

Consented patients who withdraw consent prior to randomization, or who are found not to meet the inclusion/exclusion criteria prior to randomization will not be included in the Intent-to-Treat population. The primary analysis will consist of all available data evaluated under Intent-to-Treat principles, referred to in ICH E9 ("Statistical Principles for Clinical Trials") as the *full analysis set*. An "as treated" analysis will also be performed which will report results based on treatment actually received.

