7 RISKS / BENEFIT ASSESSMENT

Both the MILD and CMM treatments carry risks of complications with the procedure and recovery. This study is considered an evaluation of marketed treatments, neither of which is a 'study' or 'investigation'.

MILD offers an option for LSS patients experiencing symptoms refractory to more conservative therapies. The Vertos MILD devices were cleared by the FDA for marketing in the USA in December 2006 under a 510(k). Procedural risks are reduced by physician training and by performing the procedure under direct fluoroscopic visualization. The MILD devices are radiopaque to provide ease of x-ray imaging and placement within the body during the procedure. Conformance with the product labeling and instructions for use will minimize these risks.

Potential risks and benefits for all therapies offered in this study are listed in Table 2.

Table 2: Procedure Risks and Benefits

Therapy	Benefits	Risks/Side Effects
---------	----------	--------------------

Physical Therapy (PT): Passive PT includes heat and cold therapy, Iontophoresis, tens, and ultrasound. Active PT includes exercise and stretching.¹³
	
 Non-surgical therapy that may provide relief of lower back and limb symptoms in patients with neurogenic claudication Muscle strengthening Correction of posture Reduction of inflammation Reduction of muscle spasms 	
 Fatigue Muscle ache Increase lower back Soreness Swelling Increase in localized pain Decrease in immunity due to the suppressive effect of the steroid

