8.5 REPORTING OF ADVERSE EVENTS

Subjects will be carefully monitored during the study for possible AEs. Any AE observed should be fully evaluated by the investigator. Collection of related AEs and all SAEs will

commence from the time the patient has the study procedure. Routine collection of AEs will continue until Study Completion or Termination visit.

At each study visit, the investigator will assess whether any device/procedure related AEs or SAEs have occurred. Subjects may report AEs occurring at any other time during the study.

All subjects experiencing AEs, whether considered associated with the device and/or procedure or not, must be monitored until the symptoms subside and have returned to baseline or until there is a satisfactory explanation for the changes observed. All AEs will be documented on the Adverse Event CRF, when the investigator concludes the event to be either possibly or definitely related to the study device/procedure, and/or the AE is serious. The event term, start and stop date and severity will be documented, along with the investigator's opinion of the nature of the causal relationship between the event and the device/procedure.

UADEs have special reporting requirements. investigator and sponsor will follow adverse device effects reporting requirements per CFR Title 21 Part 803:

Investigator Report: If a subject experiences an UADE, the investigator must notify sponsor within 24-hours of receiving knowledge of the event, and the IRB/EC as soon as possible, but no later than the deadline specified by IRB/Ethics Committee (EC) reporting policy.

Sponsor Report: UADEs will be reported to FDA, all reviewing IRB/ECs, and participating investigators as soon as possible, but no later than 10 working days, after receiving notice of the UADE(s).

As with any AE outside of the study, all AEs should be followed up until resolution or until the investigator judges that further follow-up is not necessary.

The investigator must follow their local IRB policy for AE reporting. Such events may be reportable to the FDA under the Medical Device Reporting Regulation. Product complaints related to the MILD devices will be documented and investigated per Vertos quality policy.

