9 GENERAL STATISTICAL METHODOLOGY

All subjects who are treated will be evaluated for safety regardless of whether or not the procedure is aborted or the patient withdraws prior to the completion of all post-treatment evaluations.

Continuous data will be summarized using descriptive statistics: mean, standard deviation, median, minimum and maximum. Categorical variables will be summarized using frequency counts and percentages. For events which can occur more than once in a single subject (e.g., adverse events), the percentage will be based on subjects experiencing the event, and both patient and event counts will be reported. All hypothesis testing will be performed using a two-sided test at a 0.05 level of significance or a one-sided test at a 0.025 level of significance.

Data will be analyzed on an intent-to-treat (ITT) basis, under which analyses will be performed according to randomized assignment irrespective of the treatment actually received.

Consented patients who withdraw consent prior to randomization, or who are found not to meet the inclusion/exclusion criteria prior to randomization will not be included in the ITT population. The primary analysis will consist of all available data evaluated under ITT principles, referred to in ICH E9 (“Statistical Principles for Clinical Trials”) as the full analysis set. An as-treated analysis will also be performed for the primary efficacy endpoint which will report results based on treatment actually received irrespective of randomization.

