- Dated and signed notes in the subject's medical record on the day of entry into the study that identify: signed study Informed Consent, the participant's date of entry into the study, the study sponsor, the clinical site, the subject number assigned and a statement that informed consent was obtained. It must be possible for the investigator and the hospital personnel to identify each patient by using this participant's file. If the participant's data is recorded electronically, the investigator should assure hard-copies are filed on a regular basis.
- Dated and signed notes from each study participant visit with reference to the CRFs/eCRFs for further information, if appropriate (for specific results of procedures and exams).
- Completed study questionnaire surveys.
- Notes regarding narcotic and non-narcotic analgesics taken during the study.
- Documentation of co-interventions used during the study.
- Study participant's condition upon completion of or withdrawal from the study.
- Documentation is required to show reasons patients failed screening, along with their signed informed consent form.

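### Serious device/procedure-related adverse events are tabulated only by randomized group in the readable plan, so a MILD-related event in a CMM-assigned subject who received MILD would count under CMM

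*Combined protocol and SAP*

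**What the plan says.** Section 9.2 defines the safety endpoint as the incidence of serious adverse events related to the device or procedure, classified by an independent adjudicator. It then fixes the grouping: "This endpoint will be tabulated and reported by randomized group". The same section promises a summary of all reported adverse events and gives no grouping for it.

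Section 9 says who is assessed: "All subjects who are treated will be evaluated for safety regardless of whether or not the procedure is aborted or the patient withdraws". That settles who is included but not the column in which a subject is counted. The general rule in Section 9 is analysis by assignment, with one exception: "An as-treated analysis will also be performed for the primary efficacy endpoint which will report results based on treatment actually received irrespective of randomization".

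The synopsis words the exception more broadly. Its as-treated "analysis will also be performed which will report results based on treatment actually received", with no endpoint named.

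Section 7 describes the setting: "This study is considered an evaluation of marketed treatments", and "MILD offers an option for LSS patients experiencing symptoms refractory to more conservative therapies".

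On data capture, Section 8.5 states "The event term, start and stop date and severity will be documented", together with the investigator's causal opinion. Section 11.1 lists among the source records "Documentation of co-interventions used during the study".

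**The concern.** An endpoint defined by its relation to a device or procedure is naturally read as a rate among people who had that procedure. A table by assignment answers a different question as soon as anyone assigned to CMM receives MILD. Any MILD-related serious event in such a subject is then added to the CMM count and is missing from the MILD count, so one event moves both columns in opposite directions.

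Two features make this worth settling in advance. Serious related events are likely to be few in a trial of about 150 subjects, so one event is a large share of the total. Also, CMM includes injections and other procedures with serious risks of their own (Section 7, Table 2), so a nonzero CMM cell would not look odd. The summary table alone would not show whether an event came from an injection or from a later MILD procedure.

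**Working it through.** **Plan's own figure.** The plan states no safety rate, event count or crossover rate, so there is nothing to reproduce. The check is one of text, followed by an illustration.

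**Text, side by side.**
- Section 9.2: this endpoint is grouped by assignment.
- Section 9: as-treated analysis for the primary efficacy endpoint only.
- Synopsis: as-treated analysis, endpoint not named, safety not mentioned.
- Sections 6.4 and 6.5 and the rest of the readable text: no crossover rule and no safety table by treatment received.

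The readable plan therefore gives one safety grouping, by assignment, and two different scopes for the as-treated analysis.

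**Inputs for the illustration.** From the plan: up to 150 subjects (Section 5.1), randomized 1:1 (Section 6.2), so 150/2 = 75 per arm. Assumed:
- all 75 MILD-assigned subjects receive MILD;
- c = 1 to 8 CMM-assigned subjects receive MILD;
- m = 2 related serious events occur in the MILD arm;
- one MILD-related serious event occurs among the c subjects, after the procedure;
- no CMM-related serious events occur.

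**By randomized group.** MILD m/75 = 2/75 = 2.7%. CMM 1/75 = 1.3%.

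**Among all subjects given MILD.** (m + 1)/(75 + c):
- c = 1: 3/76 = 3.9%
- c = 2: 3/77 = 3.9%
- c = 4: 3/79 = 3.8%
- c = 8: 3/83 = 3.6%

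The CMM column by receipt is 0/75 if every CMM-assigned subject contributes the time before any MILD procedure. The c subjects then stand in both denominators with unequal follow-up, so these percentages are not a like-for-like comparison. If only subjects never given MILD are counted, the denominator at c = 8 is 75 - 8 = 67.

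**Precision.** Exact (Clopper-Pearson) 95% intervals: 2/75, 0.3% to 9.3%; 3/76, 0.8% to 11.1%; 3/83, 0.8% to 10.2%. They overlap almost entirely.

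**Sensitivity to m and to CMM events.**
- m = 1: 1/75 v 1/75 (1.3% v 1.3%) by assignment; 2/76 to 2/83 (2.6% to 2.4%) v 0/75 by receipt.
- m = 0: 0/75 v 1/75 (0% v 1.3%) by assignment; 1/76 to 1/83 (1.3% to 1.2%) v 0/75 by receipt. The direction changes, but only because CMM-related events were set to zero.
- m = 0, c = 1, plus one CMM-related event: 0/75 v 2/75 by assignment; 1/76 v 1/75 (1.3% v 1.3%) by receipt, so no MILD excess appears.

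**How likely is even one such event?** With risk p per crossed-over subject, the chance is 1 - (1 - p)^c. For assumed p of 1% to 5%, this runs from 1% (c = 1, p = 1%) to 33.7% (c = 8, p = 5%). If half of the CMM arm crossed over (c = 38), p = 5% gives 85.8%. The plan gives no basis for choosing among these values.

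**The case against.** The strongest reply is that the harm depends on crossover, which no readable passage describes. The places where it would be described (treatment, follow-up, schedule, and the table after the safety text in Section 9.2) are partly blacked out or missing. What can be read points the other way: the control is CMM without MILD, subjects are treated as randomized (Section 6.4), the medical monitor handles questions about prohibited procedures (Section 10.2), and the protocol must be followed as written (Section 13.5). This stands as a limit on frequency, which is unknown. It does not remove the point, because both as-treated sentences exist only for the case in which treatment received differs from assignment.

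Second, every complication is independently classified (Section 10.3), and causal opinion and dates are recorded, so an event could be traced to MILD. That is true of the individual event, but tracing it does not change the column in which it is counted.

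Third, the synopsis sentence can be read to cover safety. It can, but it names no safety table, and Section 9 narrows it.

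A reader might infer three stronger things that the documents do not support:
- *That crossover to MILD is planned or expected.* Section 7 is general background on a marketed device, not a statement about control subjects.
- *That the randomized table would show the wrong direction of risk.* This follows only under the assumed counts, with no MILD-arm event and no CMM-related serious event.
- *That MILD-assigned subjects who never had MILD would leave the safety set and raise the MILD rate further.* The MILD arm also receives CMM, so such subjects are still treated in the sense of Section 9.

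**Conclusion.** The point holds as a conditional gap in reporting. Section 9.2 states a grouping rule that would place a MILD-related serious event in a CMM-assigned MILD recipient under CMM. No readable passage supplies the complementary table, and the synopsis and Section 9 differ on whether the as-treated analysis could cover it.

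Under the stated assumptions, with 2 MILD-arm events, a displayed 2.7% becomes 3.6% to 3.9% among all subjects given MILD. Any CMM-related serious events would lessen the contrast between columns by receipt. This is a matter of displayed rates; no test is affected. With no departures from assignment the two tables agree, and redacted text may already deal with the matter. It is an improvement to consider, held with medium confidence.

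**What to change.** Keep the randomized-group table in Section 9.2 and add one table of serious device- or procedure-related adverse events by treatment actually received:
- The MILD group is every subject in whom MILD was attempted, including aborted procedures, in line with the inclusion rule in Section 9.
- For a CMM-assigned subject who received MILD, events before the procedure count under CMM and events from it onward under MILD.
- A footnote says that these subjects contribute to both columns and how many there are.
- Follow-up time and events per person-time stand beside the percentages, because exposure in the two columns is unequal.

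Reconcile the as-treated sentences in the synopsis and Section 9 so that both say whether safety is covered. If redacted text already specifies such a table, the sponsor need only confirm it and align the two sentences.

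The cost is one table and a few sentences. The procedure date of any crossover must be available for analysis; a co-intervention note in the medical record does not by itself ensure that. The by-receipt comparison is not randomized and should be labelled so. The MILD rate may look slightly less favourable.

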10 STUDY GOVERNANCE

10.1 STUDY PRINCIPAL INVESTIGATOR (SPI)

During the course of the study, the SPI will:

- Oversee clinical trial activities including protocol development, and any changes that may be desired or required during conduct of the study.
- Assist in obtaining evaluation and feedback from peers throughout the course of the study.
- Review and approve protocol and site selection.
- Register the study protocol on ClinicalTrials.gov prior to enrollment of first patient.
- Direct and support site investigators.
- Perform comprehensive periodic review and assessment of patient enrollment, study data and protocol compliance.
- Oversee safety of adverse event reporting.
- Report study results on ClinicalTrials.gov within 1 year of study completion.
- Support publication of study results in peer-reviewed journal within 1 year of study completion.

10.2 MEDICAL MONITOR (MM)

The MM will be an Individual who is knowledgeable in the appropriate disciplines and medical specialties pertinent to the disease state being evaluated in this clinical Study. The MM will be a qualified medical practitioner who has experience and training in the MILD device and procedure. During the course of the study, the MM will:

- Review all subject medical records, baseline imaging to confirm the diagnosis and the appropriate level(s), Measure the thickness of ligamentum flavum at the treatment level(s). Also, ensure that eligibility criteria are met prior to randomization.
- Monitor overall study safety.
- Approve patient enrollment including review of MRIs.
- Respond to patient safety related inquiries from members of the Clinical Team including, but not limited to: patient eligibility, prohibited medications or procedures, exclusionary medical history, adverse events, and protocol deviations that impact patient safety.
- Participate in protocol development and amendment review.

- Perform comprehensive periodic review and assessment of patient enrollment, study data and protocol compliance.
- Prepare and/or review SAE narratives if applicable.
- Ensure adequate documentation of safety decisions.
- Escalate safety events as necessary.
- Consult with other study advisors as needed for safety issues requiring additional input.
- Support publication of study results in peer-reviewed journal within 1 year of study completion.

10.3 CLINICAL EVENTS ADJUDICATOR (CEA)

The CEA will be an individual who is independent of the Investigational Sites. The CEA will be responsible for the review and validation of all complications that occur over the course of the Study and the subsequent classification of these complications as related to the device or procedure. The CEA will review all complications and adjudicate them as defined in Section 8: Adverse Events. The CEA can request additional source documentation and any available imaging to assist with adjudication.

11 STUDY MANAGEMENT

11.1 SOURCE DOCUMENTATION

All required data for this study is to be recorded in the subject's medical chart for source documentation and data verification. Clinical research coordinators (CRC) at each site will perform primary data collection from source documents (reviews prior to transcribing onto Case Report Forms (CRFs), or eCRFs. Source data includes original records of clinical findings, observations, or other activities in a clinical trial. Examples of these original documents and data records include: hospital records, clinical and office charts, laboratory notes, memoranda, subjects' diaries or evaluation checklists, pharmacy dispensing records, recorded data from automated instruments, copies or transcriptions certified after verification as being accurate and complete, microfiches, photographic negatives, x-rays, and subject files.

The investigator is ultimately responsible for the integrity of the data recorded and submitted on the CRFs/eCRFs; therefore, each CRF/eCRF must be reviewed and signed by the investigator. To protect subject confidentiality, the subject's name must not appear anywhere on the CRF/eCRF, and must be removed or redacted from any supporting documentation. Each page should be identified with the subject's study ID number and initials only. All other subject identifiers (e.g. medical record number, social security number) are to be obscured. CRFs/eCRFs will be completed in a timely fashion.

Regulations require that investigators maintain information for every subject participating in the clinical study, in the study subject's medical records that corroborate data collected on the CRFs/eCRFs. In order to comply with these regulatory requirements, the following information will be maintained and made available as required to monitors and/or regulatory inspectors:

- Medical history and physical condition of the study subject before involvement in the study sufficient to verify protocol entry criteria (if not already present).
- Dated and signed notes in the subject's medical record on the day of entry into the study that identify: signed study Informed Consent, the participant's date of entry into the study, the study sponsor, the clinical site, the subject number assigned and a statement that informed consent was obtained. It must be possible for the investigator and the hospital personnel to identify each patient by using this participant's file. If the participant's data is recorded electronically, the investigator should assure hard-copies are filed on a regular basis.
- Dated and signed notes from each study participant visit with reference to the CRFs/eCRFs for further information, if appropriate (for specific results of procedures and exams).
- Completed study questionnaire surveys.
- Notes regarding narcotic and non-narcotic analgesics taken during the study.
- Documentation of co-interventions used during the study.
- Study participant's condition upon completion of or withdrawal from the study.
- Documentation is required to show reasons patients failed screening, along with their signed informed consent form.

